9.6.2. Description of comparator(s)

This group will undertake a routine course of one to one out-patient physiotherapy over 12 weeks. To allow comparison between the two groups the control group will also have up to four review appointments where their home exercise programme can be progressed or regressed. The physiotherapy treatments will not be restricted (apart from no BW programme) to allow for a pragmatic approach based on the treating clinician's clinical judgement, however their content will be recorded on treatment logs.

9.7. Baseline Assessments

After written informed consent is taken, the baseline assessment measurements will commence. The research clinician will take general demographic information, relevant medical history, falls history, type of arthroplasty and height and weight. They will then carry out the following physical measures:

BBS – The BBS is a validated measure of balance for patients with osteoarthritis with normative data for post hip and knee replacement available¹⁹. The participant is asked to complete fourteen different balance test including sit to stand, stand to sit, unsupported standing, unsupported sitting, transfers, standing with eyes closed, standing with feet together, reaching forward, picking up an object from the floor, turning to look behind, 360 degree turn, step onto stool, tandem stance and single leg stance. Each task is marked out from 0 to 4 with 4 being the best score. The test is totalled out of 56 with higher scores indicating lower falls risk.

FSST - This clinical test is a valid and reliable measure of dynamic balance in older adults²⁰. The participant is timed during multi-directional stepping into four different quadrants separated by walking sticks. The participant will step forward over a stick, step to the right sideways over a stick, step backwards over a stick and step to the left sideways over a stick; the sequence will immediately be repeated in reverse. The participant will start over if he/she touches a stick with his/her foot or if it is completed in the wrong sequence. The total time taken to complete this test will be recorded.

2MWT – Provides a measure of gait speed and distance²¹. The participant will walk 20-metre laps for two minutes. The distance completed during the two minutes will be recorded to provide a measure of endurance. Assistive devices can be used but must be consistent between testing.

30s Chair rise test – This is a validated clinical measure of lower body strength and dynamic balance which is recommended as one of the best physical performance tests following joint arthroplasty by OARSI²². The participant is asked to sit in a straight back chair of 17" seat height without arms. From the sitting position, the participant stands up completely up so hips and knees are fully extended, then completely back down, so that the bottom fully touches the seat. This is repeated for 30 seconds and the participant should not use their hands to get up. If the participant is unable to do this they are allowed to place their hands on their knees or use their regular mobility aid to rise from the chair and this is recorded as an adapted score.

Following the collection of the physical outcome measures the participants will be asked to complete the ABC questionnaire. This provides a measure of balance confidence whilst performing certain tasks and is a 16 item self-report measure. Each question is scored out of 100 with 0 representing no confidence and 100 representing total confidence. The average of all scores is used to provide a final score and normative data is available for older adults²³.

At the end of the assessment the participant will be issued with a falls diary to complete for the 3 months whilst they are taking part in the study. For those randomised to the intervention arm a diary of adherence to the BW programme will also be issued at the initial physiotherapy appointment.

9.8. Subsequent Visits

As this is a feasibility pilot study the main aims are not to assess the effectiveness of the intervention but to trial the acceptability and feasibility of the study protocol and pilot its delivery at the Nuffield Orthopaedic Centre in Oxford. For this reason the main assessments for the study relate to recruitment, retention and acceptability. The research clinician will therefore collect data throughout the trial on the number of patients screened, the number that consented, the reason for not consenting, the number of drop outs, the availability of the outcome measure data and the standard deviation of the BBS in order to estimate the sample size. The acceptability of the intervention will be measured through collection of the BW programme diary which will provide a measure of adherence. Participants will also be invited to take part in an interview to determine the study acceptability.

Fidelity checks

Fidelity checks will be made by a member of the study team who is not blinded to treatment allocation to ensure adherence to the study protocol from the recruiting and treating clinicians. These will take place mid-way through study recruitment once approximately 20 participants have been randomised.

12 week follow up

Participants will be followed up at 12 weeks for the final assessment. Participants will be asked to return to the physiotherapy clinic or where possible this appointment will tie in with their final physiotherapy appointment at 12 weeks. The outcome measure assessments will be the same as at baseline and the research clinician will ensure they collect in the falls diary and if applicable BW programme diary.

Qualitative interviews

Patients taking part in the study, and treating clinicians, will be invited to take part at the in a semi-structured interview to determine if the study procedures and trial design were acceptable to participants. This will take place after the participants have completed their 12 week follow up and physiotherapists have completed the intervention delivery.

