3. SYNOPSIS

Study Title	A Backwards Walking Programme following Hip and Knee Arthroplasty: A Feasibility Pilot Study		
Internal ref. no. / short title	Backwards Walking in patients following Knee and Hip Replacement		
Study registration			
Sponsor	Oxford University Hospitals NHS Foundation Trust		
Funder	N/A		
Study Design	Mixed methods feasibility pilot study		
Study Participants	Men and women who have undergone hip or knee arthroplasty		
Sample Size	40 participants/ 20 per group		
Planned Study Period	12 months total length/ individual participant involvement 3 months		
Planned Recruitment period	01/03/2020 to 01/09/2020		
	Objectives	Outcome Measures	Time point(s)
Primary	To test the procedures and processes of the trial and to estimate parameters for the main trial sample size calculation	
 • Berg Balance Scale • Participant recruitment figures • Participant retention figures • Number of protocol violations • BW programme diary • Qualitative interviews 	Baseline and 3 months
Secondary	To examine the consistency of the effects of the backwards walking programme on falls risk, balance, strength and gait speed following hip and knee joint arthroplasty	
 • Four Square Step Test • 2 minute walk test • 30 second stand test • Activities-specific Balance confidence scale • Falls diary 	Baseline and 3 months
Intervention(s)	A 12 week backward walking programme alongside a standard course of physiotherapy		
Comparator	Standard course of physiotherapy		

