BW is a form of closed kinetic chain exercise which is known to be more functional, safe and effective than open kinetic chain exercises due to the reduced compressive forces at the patellofemoral joint⁹. Compared to forward walking, lower limb muscle activity during backward walking is greater due to the higher recruitment of motor units¹⁰. In addition, BW has been seen to increase cardio-pulmonary demand¹¹ helping to improve the cardiovascular fitness of patients. The absence of visual cues also increases the spatial and temporal gait parameters¹². BW does not require any specific equipment thus is a cost effective and easy mode of rehabilitation. Additionally once it has been completed under supervision a BW programme can be continued as part of a home exercise programme. Taking into consideration all of these factors BW could form an important functional and strengthening role in the rehabilitation of patients post THA and TKA/UKA.

There have been a number of studies looking at BW for different musculoskeletal conditions. A recent literature review and meta-analysis concluded that although there was sufficient evidence to recommend a BW programme as part of a rehabilitation programme for patients with knee osteoarthritis, other conditions still required further evidence¹³. Patients following hip and knee arthroplasty differ from the populations with knee OA as they have greater strength deficits¹⁴ and lower activity levels post operatively¹⁵ making them more at risk of falls. To date there are no randomised controlled trials (RCT) looking at a BW programme for this population. It is therefore pertinent that we look at the effectiveness of BW post hip and knee arthroplasty in reducing the risk of falls and improving balance and physical function in a RCT. This feasibility pilot will be the first step to delivering the RCT and will test the procedures and acceptability of a BW programme for patients following THR/TKA/UKA.

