6. OBJECTIVES AND OUTCOME MEASURES

Objectives	Outcome Measures	Timepoint(s) of evaluation of this outcome measure (if applicable)

Primary Objective To test the procedures and processes of the trial and to estimate parameters for the main trial sample size calculation
	
 • Berg Balance Scale (BBS) (to calculate sample size) – Static and dynamic balance activities of varying difficulty are performed to provide a measure of falls risk and balance • Participant recruitment figures • Participant retention figures • Randomisation acceptability • Number of protocol violations from fidelity checks • BW programme diary to provide a measure of adherence • Participant safety through recording any falls and injuries whilst completing the BW programme • Qualitative interviews to determine acceptability of intervention and delivery with participants and physiotherapists 	Baseline and 3 months

Secondary Objectives To examine the consistency of the effects of the backwards walking programme on falls risk, balance, strength and gait speed following hip and knee joint arthroplasty
	
 • Four Square Step Test (FSST)- a test of dynamic balance that clinically assesses a person's ability to step over objects forward, sideways, and backwards • 2 minute walk test (2MWT)- assesses walking distance • 30 second chair rise test - assesses sit to stand ability and provides a measure of lower limb strength and dynamic balance. • Activities-specific Balance confidence scale (ABC) - self-reported measure of confidence in performing various ambulatory activities without falling • Falls diary - records the frequency of falls 	Baseline and 3 months

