9.6. Description of study intervention(s), comparators and study procedures (clinical)

9.6.1. Description of study intervention(s)

This group will undertake a routine course of one to one out-patient physiotherapy which will include a BW programme. The BW programme will be prescribed by a physiotherapist and the participant will carry it out, along with other prescribed exercises, in their own home. Aside from the BW programme the physiotherapy treatments offered in the initial and review sessions will not be restricted but will be recorded in treatment logs. Each participant will initially be prescribed a 5 minute BW programme to be completed once a day. Participants will score the intensity of their backwards walking based on the BORG rating of perceived exertion scale. The aim will be for participants to be working at the light to somewhat hard level on the scale (11-14) (see appendix 1). The length of the BW programme and intensity will be progressed or regressed as deemed appropriate by the treating clinician with the aim for patients to achieve at least 10 minutes of BW every day of the week by the end of the programme. The

programme will be issued for completion over the course of 12 weeks and up to four review appointments will be made with the participant to monitor the BW programme and other prescribed exercises. To promote adherence a BW programme diary will be issued to participants to complete each time they carry out the programme in their own homes.

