11.2. Description of the Statistical Methods

This is a feasibility pilot RCT, therefore the aim of this study is not to provide a measure of efficacy but to determine whether it is possible to run a large scale RCT. Participant demographics will be summarised using standard descriptive statistics. The following components will also be analysed:

- The mean and SD of the primary outcome measure the BBS will be analysed to provide a sample size calculation for a larger RCT
- Recruitment – The number of recruited participants in the recruitment window, the number of participants screened to allow for the recruitment target to be met and the reason for non-entry into the trial which will provide realistic expectations of recruitment for a future larger scale RCT.
- Randomisation – Is randomisation acceptable to participants in this study? Does randomisation create comparable groups?
- Intervention acceptability – Is the intervention acceptable to participants? Do any participants fail to complete the intervention? Adherence to the prescribed BW programme will be measured through a collection of a diary. These issues will also be explored in more depth as part of the qualitative study.
- Retention of participants – Drop outs and wherever possible the reason for drop out will be recorded.
- Fidelity - Fidelity checks will be conducted, this will involve observing treatment sessions to check adherence to the protocol.

Qualitative interviews:

The data from the interviews will be analysed using thematic analysis, using six steps proposed by Braun and Clarke transcribing the data, generating initial codes, searching for themes, reviewing themes, defining and naming themes and producing the report. Data will be transcribed from the audio recordings, whilst initial ideas are recorded. Then data will then be coded, before codes are grouped into themes. To aid the process of data analysis NVIVO 10 (or later version) software will be used, this computer programme is designed for the analysis of qualitative data. It allows the collection, sorting and analysing of data from qualitative methods such as interviews.

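### The protocol-violation count is taken only from sessions observed at one mid-recruitment stage, although treatment logs in both arms and the deviation forms span the whole study and have no planned use in it

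*Combined protocol and SAP*

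**What the plan says.** Section 6 lists "Number of protocol violations from fidelity checks" among the outcomes for the primary objective. The synopsis (section 3) lists the same outcome as "Number of protocol violations", without tying it to any source.

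Section 9.8 says that a team member who knows the allocation does the checks, and that their purpose is "to ensure adherence to the study protocol from the recruiting and treating clinicians". On timing it says: "These will take place mid-way through study recruitment once approximately 20 participants have been randomised". Section 11.2 gives the method: "Fidelity checks will be conducted, this will involve observing treatment sessions to check adherence to the protocol". No section gives the number of sessions, the arms to be observed, a definition of a violation, or a denominator.

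Two other records exist:

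- **Treatment logs.** For the intervention arm, section 9.6.1 says that, backwards walking aside, "the physiotherapy treatments offered in the initial and review sessions will not be restricted but will be recorded in treatment logs". For the control arm, section 9.6.2 says "The physiotherapy treatments will not be restricted (apart from no BW programme" and closes the bracket there; it then requires session content to be logged as well.
- **Deviation forms.** Section 14 asks for every departure from the protocol to be written up on a form and filed, with no limit by time or arm.

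Section 11.2 gives neither record a role in the analysis.

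**The concern.** The pilot exists to find out whether the trial procedures work and whether a large trial is possible. That depends on whether the programme was delivered in one arm and withheld in the other. As defined in section 6, the violation count describes only what was seen in an unstated number of sessions at one point. A low or zero count could then be read as evidence of good delivery when it says little about the rest of the study.

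Separation of the arms deserves particular attention. Participants and treating clinicians cannot be blinded (section 9.5), and section 5 notes that "BW does not require any specific equipment". The only restriction on control treatment is that it contains no backwards walking programme, yet no analysis tabulates breaches of that restriction. Home practice by controls is not asked about in any planned quantitative measure, because the backwards walking diary goes to the intervention arm only (section 9.7).

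**Working it through.** **Inputs from the protocol.** 40 participants, 20 per group (section 11.3); checks at about 20 randomised (section 9.8); at most four reviews per participant in each arm (sections 9.6.1 and 9.6.2); an initial session in the intervention arm (section 9.6.1).

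**Assumptions.** One initial session for controls too, which section 9.6.2 does not state. The number of observed sessions k and the true violation rate p per session are not in the protocol, so ranges are shown.

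**Step 1: the plan's own figure.** Mid-way is 40 / 2 = 20, which agrees with section 9.8.

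**Step 2: sessions available.** The maximum is 40 × (1 + 4) = 200, or 100 per arm. Without initial sessions it is 40 × 4 = 160. Both are ceilings.

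**Step 3: what one stage can reach.** Participants 21 to 40 account for up to 20 × 5 = 100 sessions, half of the maximum. Checks made when about 20 have been randomised come before most or all of these. Sessions that earlier participants have already attended cannot be observed either.

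**Step 4: coverage.** Coverage is k / 200:

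- k = 5: 5/200 = 2.5%
- k = 10: 10/200 = 5%
- k = 20 (one per participant randomised by then): 20/200 = 10%

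**Step 5: chance that the checks show no violation.** With independent sessions this is (1 − p)^k:

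| p | k = 5 | k = 10 | k = 20 |
|---|---|---|---|
| 5% | 77% | 60% | 36% |
| 10% | 59% | 35% | 12% |
| 20% | 33% | 11% | 1% |

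At p = 10% there would be 200 × 0.10 = 20 violations in the study. The checks would count k × 0.10 = 0.5, 1 or 2 of them on average.

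**Step 6: what a zero count would exclude.** The one-sided 95% upper limit after zero violations in k sessions is 1 − 0.05^(1/k). This is 45%, 26% and 14% for k = 5, 10 and 20.

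If violations cluster by therapist, independence fails. At the same average rate, positive clustering makes a zero count more likely than the table shows.

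**The case against.** The strongest reply is section 14. Any recognised deviation is documented whenever it occurs, in either arm, and backwards walking given to a control in a session should also appear in that participant's log. This stands. A reader might infer that most violations go unrecorded, but the documents do not support that. For recognised or logged breaches, the gap is that nothing carries them into the outcome or the analysis.

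A reader might also infer that there is only a single observation. The text uses the plural for both checks and sessions. What is single is the stage of the study, and the number of sessions is unstated. With 20 sessions, the chance of missing a 10% violation rate falls to 12%, so a conclusion based on 5 or 10 sessions alone would show only the unfavourable end.

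A third tempting inference is that contamination would enlarge the main trial. The usual factor 1/(1 − c)² gives 1.23, 1.56 and 2.04 for c = 10%, 20% and 30%. The protocol gives no contamination rate and describes no such adjustment. The formula also supposes that each contaminated control gains the full effect of the programme. These factors therefore do not measure this defect.

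Finally, violations are one of eight measures under the primary objective. Section 11.2 calls the Berg Balance Scale the primary outcome measure, and section 9.8 puts the emphasis on recruitment, retention and acceptability. That limits the weight of the point but does not answer it.

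**Conclusion.** The concern holds as a defect in how a feasibility outcome is ascertained. Section 6 confines the count to observed sessions at one mid-recruitment stage, with no number, arms or denominator. Records spanning the study are kept but not used, and the synopsis gives the same outcome a wider scope.

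If no more than 20 sessions are observed, at least 90% of the 200-session maximum lies outside the count. That rests on the assumed initial control session and on full attendance. The chances of a zero count rest further on the assumed violation rates and on independence. The documents do not establish how many violations would be missed. The improvement is cheap and worth making; it does not affect the validity of the pilot or its sample size.

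**What to change.** 1. Redefine the outcome in section 6 as violations in all randomised participants, by arm and with denominators (sessions and participants), taken from the treatment logs and the section 14 forms. From the logs, count backwards walking given to a control, and backwards walking not prescribed or not reviewed in the intervention arm. Section 9.6.1 leaves it unclear whether the log covers the backwards walking programme itself, so the log should carry an explicit item for it in both arms.
2. Keep the mid-study observation as a check on log accuracy and on recruitment procedures, which treatment logs cannot show. State how many sessions will be observed and in which arms.
3. Add this tabulation to section 11.2, and give the outcome the same scope in the synopsis and section 6.
4. Optionally, ask controls one question about backwards walking at home. Ask it only at week 12, because asking earlier may prompt the behaviour. Return it to the unblinded team member and not with the falls diary, which the research clinician collects (section 9.8) and who must stay blinded (section 9.5).

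**Cost.** Some extra data abstraction, which the unblinded team member who already makes the checks could do. A limitation remains: the logs appear to be completed by the clinicians whose adherence is being assessed, which is why the observation should be kept.

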2. LAY SUMMARY

Backwards walking has been shown to improve balance and walking in patients who have knee Osteoarthritis. We don't know if these benefits may also be seen after surgery with patients who have had a hip or knee replacement because of Osteoarthritis. This study will look to see if it is possible to conduct a bigger study into how effective backwards walking may be after joint replacement. Patients who come to the Nuffield Orthopaedic Centre in Oxford for a hip or knee replacement will be invited. They will be placed into one of two groups at random: a group where they have a course of physiotherapy plus a backwards walking programme or a group where they have a course of physiotherapy. The physiotherapy will last for 12 weeks and those who take part will take part in two study assessments. The first will be before any treatment and patients will complete five measures and also be issued with a simple tick box diary to complete over the 12 weeks. The second assessment will be after the treatment and will involve the same 5 measures and the diaries will be collected in. Participants at this assessment will also be asked if they would like to take part in an interview for the study. This is to see what the patients thought of the study. During the study the researcher will record things like how many patients say 'yes' to the study and how many participants drop out of the treatment to understand if a bigger study could take place.

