9. PROTOCOL PROCEDURES

9.1. Recruitment

Patients who have had a hip or knee replacement at the Nuffield Orthopaedic Centre in Oxford attend a 6 week post discharge clinic appointment. These patients will be screened for eligibility by their direct care team (Nuffield Orthopaedic Centre Physiotherapists). They will be introduced to the study by either a letter in the post from their direct care team (which will be sent alongside their clinic appointment letter) with information about the study and invitation letter and reply slip, or they will be introduced to the study and given the study information by their direct care team during their routine clinical appointment. Patients will be given ample time to consider taking part in the study. If they express an interest in the study the investigator will review the study details and answer any questions they may have. They will then be screened for eligibility and those who meet the criteria will take part in the study. If they agree to take part an appointment will be made to obtain consent and record baseline data and outcome measures with a trial research clinician at the Nuffield Orthopaedic Centre. Once patients have completed their baseline assessment they will be randomised according to the procedure set out below. Those who do not wish to take part will be asked if they can provide a reason for declining so that recruitment onto the trial can be analysed. The trial research clinician will also record the number of responders to the study information. As detailed in the study design section after the first 5 participants have been recruited to the intervention arm the study will stop whilst adverse event data is collected to ensure participants are not falling during the intervention. Providing this is not the case the study will resume and continue to stop and evaluate adverse event data for every 5 participants in the intervention arm.

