9.5. Blinding and code-breaking

The trial research clinician who is completing the study assessments will remain blinded to the participant allocation and will not be involved in any part of the randomisation procedure to ensure that they are not able to bias the group allocation. Due to the nature of the intervention it is not possible to blind the participant or treating clinician.

As participants and treating clinicians are not blinded to the treatment allocation it is not necessary to have a code-breaking procedure.

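### Section 9.8 gives the assessor, whom Section 9.5 keeps blinded with no end point, the task of collecting a diary held only by the intervention arm, and fixes no order of collection

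*Combined protocol and SAP*

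**What the plan says.** Section 7 calls the quantitative study single blinded. Section 9.5 says whose blind that is: "The trial research clinician who is completing the study assessments will remain blinded to the participant allocation". It gives no point at which this ends. It adds that "it is not possible to blind the participant or treating clinician", so the assessor is the only blinded party it names.

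Section 9.1 arranges an appointment to "record baseline data and outcome measures with a trial research clinician". Section 9.7 describes the baseline measures as taken by the research clinician, and Section 9.8 says that the 12-week measures are the same as at baseline.

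There are two diaries. The falls diary goes to everyone: "At the end of the assessment the participant will be issued with a falls diary". The BW diary does not: "For those randomised to the intervention arm a diary of adherence to the BW programme will also be issued at the initial physiotherapy appointment". Section 9.6.2 rules out a BW programme for the control group.

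For the 12-week follow-up, Section 9.8 says "the research clinician will ensure they collect in the falls diary and if applicable BW programme diary". The lay summary (Section 2) describes the same visit as one that "will involve the same 5 measures and the diaries will be collected in".

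**The concern.** Possession of the BW diary marks a participant as belonging to the intervention arm. The qualifier attached to its collection in Section 9.8 can only mean that the participant was randomised to that arm. A clinician who has to make sure the diary is collected where it applies must receive it, ask about it, or already know the allocation. The written procedure therefore unblinds the one person whose blinding gives the study its single-blind label.

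The 12-week scores are what is at stake. The BBS is the most exposed: "Each task is marked out from 0 to 4 with 4 being the best score", so every point depends on the assessor's rating. Section 11.2 plans to use the BBS mean and SD for the sample size of the larger trial. Testing trial procedures is also part of the primary objective in Section 6, and assessor blinding is one of those procedures. An arrangement left unresolved here could be carried into the main trial.

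**Working it through.** The plan states no figure to reproduce. The check sets the sections side by side and then counts participants.

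**1. Is it the same person?** Section 9.5 refers to the trial research clinician; Section 9.8 refers to the research clinician. Section 9.1 gives the baseline assessment to the first title and Section 9.7 gives it to the second. No second assessor is described. Reading them as one role is an inference, but the natural one.

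**2. Is the diary specific to one arm?** Yes. Section 9.7 issues it only to the intervention arm, and Section 9.6.2 excludes the programme that it records from the control arm. The lay summary mentions a tick-box diary given to participants at the first assessment. That fits the falls diary and does not contradict Section 9.7.

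**3. How many allocations could be revealed?** Section 11.3 gives 40 participants, 20 per group.
- By hand-over alone: at most the intervention arm, 20 of 40.
- If the assessor asks each participant whether the diary applies, a no is also informative: 20 + (40 − 20) = 40 of 40.

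Both are ceilings. The documents give no rate of attendance or of diary return, so nothing finer can be calculated.

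**4. Is the order fixed?** No. The lay summary and Section 9.8 both mention the measures before the diaries, but only as sentence order. At baseline the falls diary is issued at the end of the assessment, but that concerns issue rather than return. Section 9.8 ties the follow-up to the final physiotherapy appointment where possible, so a participant may well arrive with the diary in hand.

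**5. Is there another safeguard?** None is stated: no other collector, no instruction to participants not to disclose their group, and no record of unblinding. Section 9.8 mentions an unblinded team member, but only for the fidelity checks midway through recruitment.

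**6. Which scores are exposed?** Section 9.7 describes the BBS as 14 tasks, each rated 0 to 4, giving 14 × 4 = 56 points, all rated by the assessor. The Four Square Step Test and the chair rise test have stated rules (a restart, full extension, an adapted score) that leave less room for judgement. The two-minute walk distance and the self-completed balance confidence scale leave little or none.

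**The case against.** The strongest reply is that the diaries are probably collected last. Both descriptions of the visit name the measures first, and Section 7 makes 12 weeks the final data collection point. If collection does come last, every participant's scores are complete before the diary appears, and the assessor's later knowledge cannot affect them. This stands as a limit on the consequence. It does not remove the conflict, because no section states the order and Section 9.5 sets no end to the blind.

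The second reply is that this is a pilot. Section 11.2 says that efficacy is not the aim and lists no between-arm efficacy test. Recruitment, retention and acceptability do not depend on the blind. This also stands, and it keeps the point modest.

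A reader might infer that the 12-week BBS scores will be biased, or that the SD carried into the main-trial sample size will be distorted. The documents support neither. Bias requires the diary to come up before scoring ends, which the plan does not prescribe. The plan also does not say which BBS SD will be used (by arm or overall, baseline or 12 weeks).

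A reader might also infer that an assessor who learns earlier allocations could predict later ones under the permuted blocks of Section 9.4. The block size is not given, so this cannot be assessed. It is at most a reason to prefer a different collector to a fixed order alone.

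**Conclusion.** The conflict between Sections 9.5 and 9.8 is real and clear on the text, given that the two clinician titles denote one role. As written, the procedure can reveal up to 20 of 40 allocations by hand-over and up to all 40 by asking, and no section supplies a safeguard. Whether any score is affected is a separate matter. That risk exists only if the diary is seen or discussed before the 12-week measures are scored, it falls chiefly on the BBS, and its size cannot be estimated. The point should be fixed because the remedy is cheap and testing procedures is part of the primary objective. It does not threaten the pilot's feasibility conclusions.

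**What to change.** **Preferred.** In Section 9.8, take BW diary collection away from the research clinician. The participant hands the diary in person, at the physiotherapy clinic visit, to the treating physiotherapist (already unblinded under Section 9.5) or to another unblinded team member. Post is a back-up only, because the diary is the adherence measure under the primary objective and posted diaries can be late or lost. The assessor collects the falls diary alone and does not ask about the BW diary.

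**Minimum.** State in Section 9.8 that the BW diary is asked for and collected only after all 12-week measures have been scored. State in Section 9.5 that the blind for each participant holds until then.

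**Cost.** The preferred change needs a reworded sentence, a small hand-over arrangement and a line telling participants where to return the diary. If that line goes into the participant information sheet, the change may need approval under Section 16.3. The minimum change costs one clause in each section and needs no new role, but the assessor still learns allocations as visits are completed.
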